9.2.4 Urine sample collection at home

A final urine sample for microscopy, culture and antibiotic susceptibility testing will be collected at home at 30 days post-randomisation, and posted to the local site laboratories via Royal Mail Safebox delivery². This home collection of urine samples will follow the standard clinical practice that is commonly utilised for children who are susceptible to recurrent infections. Universal containers containing boric acid, a preservative which increases the maximum permissible time for transport to the laboratory to up to 96 hours, will be used, in line with UK Standards for Microbiological Investigations (42). These containers will be supplied to parents/guardians at the preceding face-to-face assessment visit. The importance of filling the containers with the correct volume of urine will be explained.

9.2.5 Early urine testing

In line with standard practice, screening urine samples collected as part of clinical assessment will undergo point-of-care testing within the ED. Reading of urinalysis reagent strips may be performed manually or by using a machine analyser, in accordance with standard practice at each participating centre. As part of the inclusion criteria for CURLY, point-of-care urinalysis must demonstrate positive

² Ireland: An equivalent service will be used.

results for both nitrites and leucocyte esterase. Where urgent urine microscopy analysis is requested by the treating clinician, the presence of bacteriuria on microscopy with Gram stain is an acceptable alternative marker of likely UTI for inclusion in the CURLY trial.

9.2.6 Culture-positive UTI definition

As in clinical practice, a culture-positive UTI will be defined using these thresholds (32):

Either:

(i) Pure growth of a single organism recognised as pathogenic for UTI with the following colony count:

- ≥100,000/ml (clean catch urine or midstream urine)
 - ≥10,000/ml (catheter urine or suprapubic aspirate)

or

(ii) Growth of no more than 2 organisms. One predominant organism recognised as pathogenic for UTI with the following colony count:

- ≥100,000/ml (clean catch urine or midstream urine)
- ≥10,000/ml (catheter urine or suprapubic aspirate)

9.2.7 Testing for antimicrobial resistance and ESBL rates

We expect the majority of participants will be microbiologically cured after treatment (i.e. their posttreatment urine cultures will be negative). However, some participants may have significant posttreatment bacteriuria; possible reasons are persistence or recurrence of the original infection, or secondary infection with a different (and likely more antibiotic-resistant) bacterium. Different treatment durations may be associated with different risks of, and reasons for, failure to achieve microbiological cure.

We will investigate this first by comparing the species and antibiotic sensitivities of bacterial isolates from pre- and post-treatment urine samples. Species identification and antibiotic susceptibility testing will be performed by the local laboratories, following their routine standard operating procedures. Antibiotic susceptibilities will be reported following the European Committee on Antimicrobial Susceptibility Testing (EUCAST) breakpoint tables

(https://www.eucast.org/clinical_breakpoints; v13.0; date accessed: 03/05/2023).

We expect the great majority of Gram-negative urinary isolates in the study population to be E. coli or Klebsiella species. Cefalexin resistance in these bacteria is mainly conferred by production of ESBL. Primary outcome visit (post-treatment) isolates of Gram-negative bacteria will undergo testing for ESBL-production. All Enterobacterales isolated will be speciated using matrix-assisted laser desorption ionization time-of-flight mass spectrometry (MALDI-TOF MS) and screened phenotypically for ESBL production by subculture onto a selective indicator medium (such as CHROMagar™ ESBL, or similar). Isolates of phenotypic ESBL producers will then be stored on nutrient agar slopes and transferred to the UoB Microbiology laboratory for future studies of ESBL gene subtype.

9.3 Costs and measures of quality of life

Information on missed days of day care/nursery/school, and additional costs from a family member's time off work and/or additional paid childcare will be collected at the primary outcome assessment at 16 days post-randomisation, and at the follow-up for recurrence at 30 days post-randomisation. Data on all events and resources used among CURLY participants will be prospectively captured and will cover the use of medication and laboratory tests as well as hospital, primary care and community health services. Similarly, health outcomes in terms of duration of

illness, any subsequent hospital admission (and length of stay), relapse and mortality will be collected. This will be captured on the Primary Outcome Assessment eCRF and as required on the Change of Status and SAE eCRFs.

With the exception of the youngest children in the trial (those below 2 years of age), quality of life questionnaires (CHU9D) will be completed at baseline, at the primary outcome assessment at 16 days post-randomisation, and at the follow-up for recurrence at 30 days post-randomisation. Where appropriate, this will be self-completed (typically by children over 7 years of age). A proxy version of the CHU9D will be used for younger children and for those lacking understanding. The proxy version can also be used for children over 7 years of age if they require parental assistance. The resulting descriptive profiles will be converted into utility values using the UK tariff (40).

9.4 Acute events

Additional healthcare attendances may be necessary, for example if the child gets worse or develops potential adverse drug reactions or other clinical events. Parents/guardians will be advised to seek immediate emergency assessment with a qualified healthcare provider, preferably at the recruiting centre ED, whenever they feel this is required. Any unscheduled events will be captured retrospectively *via* the CURLY app at the "fit and well" check (48 hours after completion of the antibiotic course) and on the Day 16 primary outcome assessment eCRF and on the Day 30 questionnaire on the CURLY app.

Urinalysis and laboratory processing for culture, microscopy & antibiotic sensitivity will be performed if felt necessary by the treating clinician (i.e. where there is suspicion of clinical deterioration from the UTI, or failure of treatment). Medical judgement will be exercised in determining whether an event is an important medical event and might require special treatment or hospitalisation.

Following any acute unscheduled medical assessment, symptoms, health services utilisation and adherence (if appropriate) will be reviewed in the same way as during regular remote monitoring *via* the CURLY app. Face-to-face visits will be arranged, if necessary, with the clinical team at the recruiting centre.

9.5 Procedures to support participants and maintain patient safety

In this trial, normal pathways of care will be encouraged. However, there is a responsibility to balance this approach with the need to ensure the safety of all participants, particularly those treated for shorter durations than the current recommended practice.

Compared with standard clinical practice, additional measures for trial participants will be:

- The medicine tracker feature within the CURLY app will help parents/guardians to track medicine administration.
- Parents/guardians will be provided with a telephone contact number at their local site for any questions or concerns.
- A text/email alert will be sent to the parent/guardian on the final day of treatment, reminding them that the cefalexin is due to finish, but recommending medical review if their child's symptoms are not resolving.
- A text/email "fit and well" check will be performed 48-72 hours after the end of treatment, asking the parent/guardian to report if their child has ongoing fever or other symptoms of concern. They will be advised to seek medical advice and/or medical review if there are ongoing concerns.
- Parents/guardians will have access to the CURLY trial website throughout the duration of the trial which will suggest contacting the medical team if they have any concerns about their child.

If at any point the parent/guardian fails to respond to the text/email questionnaires, or if they
do not attend the primary outcome visit, the local study team will attempt to telephone the
parent/guardian to ensure that all is well with their child and, if necessary, to provide support
and advice.

9.5.1 Procedures for assessing safety

The CURLY app symptom checklist will explicitly prompt for known clinical adverse effects of cefalexin, which are primarily diarrhoea, rashes, and candida infections.

Additional investigations may be performed to investigate symptoms as clinically indicated. Symptom data will be monitored remotely during trial follow-up by the local clinical team.

Pre-specified clinical adverse events will be recorded on the eCRF. Serious adverse events will be defined according to Section 10.

9.6 Missing data

Every attempt will be made to collect full follow-up data on all study participants. Guidance for the following situations is given:

Participant does not attend primary outcome assessment visit:

Where the assessment visit is missed, the local research assistant will make three attempts to contact the parent/legal guardian by telephone. If contact is made, the family will be encouraged to return for their assessment. Should the family decline, they will be asked to provide information over the telephone about the child's current symptoms, use of any additional health care provider in the preceding days, and receipt of any non-trial antibiotics which will be recorded on the Change of Status eCRF. If no contact can be made with the family, the patient's GP will be contacted (after sufficient time for notification from other healthcare providers) to enquire about any consultations ± antibiotic prescriptions in the preceding days.

Post-treatment urine culture sample not provided (day 16 visit):

This would occur for the participants discussed in the previous paragraph. In addition, children will occasionally fail to provide a urine sample within an acceptable period of time. As in clinical practice, some families may choose to leave and collect the sample at home, before returning it to the hospital.

The approach to missing data analysis is discussed in Section 14.7.

9.7 Withdrawal and changes in participation

Informed consent is defined as the process of learning the key facts about a clinical trial before deciding whether or not to participate. It is a continuous and dynamic process and participants should be asked about their ongoing willingness to continue participation at all visits. Participants and/or parents/guardians should be made aware that they can freely withdraw (discontinue participation) from the trial (or part of the trial) at any time, without giving a reason and that the medical care of the child will not be affected in any way.

Participants found to be ineligible post randomisation should be followed up according to all trial processes and will still have their data analysed unless they explicitly change their level of participation.

The changes in participation within the trial are categorised in the following ways (participant and parent/guardian are used interchangeably):

No remote data collection:

The participant does not wish to complete remote data collection. They may be willing to be followed up at face to face follow up visits, or at standard clinic visits and if applicable using any central UK NHS bodies for long-term outcomes (i.e. the participant has agreed that data can be collected at standard clinic visits and used in the trial analysis, including data collected as part of long-term outcomes).

No face-to-face follow-up:

The participant does not wish to attend trial visits in accordance with the schedule of assessments. They may be willing to be followed up *via* the CURLY app or at standard clinic visits and if applicable using any central UK NHS bodies for long-term outcomes (i.e. the participant has agreed that data can be collected at standard clinic visits and used in the trial analysis, including data collected as part of long-term outcomes).

No further data collection:

The participant is not willing to be followed up in any way for the purposes of the trial AND does not wish for any further data to be collected (only data collected prior to the change in participation can be used in the trial analysis).

The details of changes in participation (date, reason, and category of status change) should be clearly documented in the source documents.

9.8 Contingency plan for follow-up visits

Visits throughout the informed consent process and beyond will take place in person at clinic, or at the participant's home, by telephone, or by video call as per local practice where patient and/or public health circumstances dictate. Where visits are in the participant's home or by telephone or video call, due care will be paid to ensure the participant is in a suitably safe and confidential environment before proceeding.

10.ADVERSE EVENT REPORTING

10.1 Definitions

Severity Definitions	Mild	Awareness of signs or symptoms that do not interfere with the participant's usual activity or are transient and resolved without treatment and with no sequelae.
	Moderate	A sign or symptom, which interferes with the participant's usual activity.
	Severe	Incapacity with inability to do work or perform usual activities.
Adverse Event	AE	Any untoward medical occurrence in a participant administered a medicinal product and which does not necessarily have a causal relationship with this intervention. Comment:

		An AE can therefore be any unfavourable and unintended sign (including abnormal laboratory findings), symptom or disease temporally associated with the use of an investigational medicinal product, whether or not related to the investigational medicinal product.
Adverse Reaction	AR	All untoward and unintended responses to an Investigational Medicinal Product (IMP) related to any dose administered. Comment: An AE judged by either the reporting Investigator or Sponsor as having causal relationship to the IMP qualifies as an AR. The expression reasonable causal relationship means to convey in general that there is evidence or argument to suggest a causal relationship.
Serious Adverse Event	SAE	Any untoward medical occurrence or effect that: Results in death Is life threatening* Requires hospitalisation or prolongation of existing hospitalisation Results in persistent or significant disability or incapacity Is a congenital anomaly/birth defect Or is otherwise considered medically significant by the Investigator**
Serious Adverse Reaction	SAR	An AR which also meets the definition of a SAE.
Unexpected Adverse Reaction	UAR	An AR, the nature or severity of which is not consistent with the applicable product information (e.g., Investigator Brochure for an unapproved IMP or (compendium of) Summary of Product Characteristics (SPC) for a licensed product). When the outcome of an AR is not consistent with the applicable product information the AR should be considered unexpected.
Suspected Unexpected Serious Adverse Reaction	SUSAR	A SAR that is unexpected i.e., the nature, or severity of the event is not consistent with the applicable product information. A SUSAR should meet the definition of an AR, UAR and SAR.

* The term life-threatening is defined as diseases or conditions where the likelihood of death is high unless the course of the disease is interrupted.

** Medical events that may not be immediately life-threatening or result in death or hospitalisation but may jeopardise the participant or may require intervention to prevent one of the other outcomes listed in the definitions above.

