10.5.2 Assessment of expectedness of an SAE by the CI

The CI or delegate will also assess all related SAEs for expectedness with reference to the criteria in Table 7: Categories of expectedness.

Category	Definition
Expected	An adverse event that is consistent with known information about the trial related procedures or that is clearly defined in the reference safety information (RSI) (section 4.8 of the Summary of Product Characteristics for cefalexin most recently submitted and approved by Medicines and Healthcare products Regulatory Agency (MHRA).
Unexpected	An adverse event that is not consistent with known information about the trial related procedures and is not listed in the RSI.

Table 7: Categories of expectedness

If the event is unexpected, it will be classified as a Suspected Unexpected Serious Adverse Reaction (SUSAR).

The CI will undertake review of all SAEs and may request further information from the clinical team at site for any given event to assist in this.

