10.6 Reporting SAEs to third parties

The independent Data Monitoring Committee (DMC) may review any SAEs at their meetings.

The Trial Office will report details of all Serious Adverse Reactions (SARs) (including SUSARs) to the MHRA, REC, and the University of Birmingham (UoB) Research Governance Team (RGT) annually from the date of the Clinical Trial Authorisation, in the form of a Development Safety Update Report (DSUR). Additionally, the Trial Office will report all events categorised as SUSARs to the MHRA, REC and RGT within the timelines required by the regulations⁴.

⁴ Ireland: SUSARs to be reported to EudraVigilance and annual listings for Ireland to the European Clinical Trials Information System.

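### Table 5 and Table 7 set different tests for an unexpected reaction, so a listed serious reaction with discordant severity or outcome is a SUSAR under one and not under the other

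*Protocol*

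**What the plan says.** Section 10.2 refers the reader to Table 5 in section 10.1 for the adverse event definitions. In that table an unexpected reaction is "An AR, the nature or severity of which is not consistent with the applicable product information", and the same entry adds: "When the outcome of an AR is not consistent with the applicable product information the AR should be considered unexpected". The SUSAR entry repeats the nature and severity test ("A SAR that is unexpected i.e., the nature, or severity of the event is not consistent with the applicable product information") and ties itself back to the other definitions: "A SUSAR should meet the definition of an AR, UAR and SAR". Because a SUSAR must also be an unexpected adverse reaction, the outcome test belongs to it too.

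Section 10.5.2 gives the operating instruction: "The CI or delegate will also assess all related SAEs for expectedness with reference to the criteria in" Table 7. There an event is expected if it is "consistent with known information about the trial related procedures or that is clearly defined in the reference safety information (RSI"), the RSI being section 4.8 of the cefalexin product summary. It is unexpected if it fails on the procedures point and is also not listed in the RSI. The section then says that an unexpected event becomes a SUSAR.

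Section 10.6 attaches the consequence: "the Trial Office will report all events categorised as SUSARs to the MHRA, REC and RGT within the timelines required by the regulations". All serious adverse reactions, SUSARs included, go into the annual Development Safety Update Report (DSUR).

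**The concern.** Expectedness is the last step in deciding how a related serious event is reported outside the trial. The protocol defines it twice, and the two definitions do not use the same attributes. Table 5 looks at nature, severity and outcome. Table 7 looks at whether the event is listed or defined in the RSI, and at whether it fits what is known about trial procedures. The person who makes the decision is sent to Table 7.

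At stake is the reporting route for a reaction that the protocol's own definitions call a SUSAR: to the MHRA and the ethics committee on the regulatory timelines, or to the same bodies in the yearly report. The participants are children aged 3 months to 11 years, most of them allocated to a duration shorter than the 10-day maximum, so a reader will expect this rule to be unambiguous.

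**Working it through.** The protocol states no figure on this point, so the check is a comparison of texts.

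**Step 1: same reference, different test.** Table 5 compares the reaction with the product information and names the Summary of Product Characteristics as the example for a licensed product. Table 7 compares it with section 4.8 of that summary. The source is in effect the same, so any difference in classification comes from the test.

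**Step 2: the logic of each test.**

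- Table 5: unexpected if nature **or** severity **or** outcome disagrees with the product information.
- Table 7, expected: fits known information about trial procedures **or** is clearly defined in the RSI.
- Table 7, unexpected: does not fit known information about trial procedures **and** is not listed in the RSI.

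**Step 3: apply both to a serious event judged related to cefalexin** (cases 1 to 4 assume that it does not fit procedure information).

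| Case | Table 5 | Table 7 |
|---|---|---|
| 1. Not listed in RSI | SUSAR | SUSAR |
| 2. Listed; severity and outcome as described | Expected | Expected |
| 3. Listed; severity beyond what is described | SUSAR | Not classed as unexpected |
| 4. Listed; outcome (for example death) not described | SUSAR | Not classed as unexpected |
| 5. Not listed, but fits procedure information | SUSAR | Expected |

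In cases 3 and 4 the event is listed, so the second of the two joined conditions for unexpected fails. The procedures condition cannot rescue it, because both conditions must hold. Cases 3 and 4 are the substantive conflict; case 5 is considered under the objection.

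**Step 4: follow the result through.** Under 10.5.2 only an event found unexpected becomes a SUSAR, and under 10.6 only a SUSAR is sent out on the regulatory timelines. Cases 3 and 4 would go into the annual report as serious adverse reactions but would not trigger that faster route.

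**Step 5: look for a tie-breaker.** Section 10.2 points to Table 5 for definitions and commits the trial to the clinical trials regulations. Section 10.5.2 names Table 7 as the criteria. Neither section, nor 10.6, says which table prevails. Severity is assessed at site, and 10.5.1 forbids the Chief Investigator to downgrade it, yet Table 7 makes no use of it.

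**The case against.** The strongest reply is that Table 5 defines and Table 7 is shorthand. Section 10.2 sends the reader to Table 5, the SUSAR entry requires the unexpected-reaction definition to be met, and 10.5.2 uses a term that has already been defined. The Chief Investigator works with reference to Table 7, reviews all SAEs and may ask sites for more information, so the step need not be mechanical matching of terms. This is a coherent reading, and a careful Chief Investigator might adopt it. It weakens the conflict but does not remove it, because no text gives Table 5 precedence and the direct instruction names Table 7.

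Three stronger readings are tempting, and the protocol does not support them.

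- A reader might infer that Table 7 asks only whether a term is listed, so that a listed reaction stays expected whatever its severity. But the expected entry requires an event "that is clearly defined in the reference safety information (RSI"), which could be read as covering severity, and it has a separate procedures limb. On that reading an atypically severe listed reaction falls into neither category. It is still not classed as unexpected, so the conflict remains, but it need not be called expected.
- A reader might infer that the procedures limb (case 5) opens a second practical route to missed SUSARs. The trial procedures are urine collection, questionnaires, an app and an optional stool sample or rectal swab. A reaction attributed to cefalexin that also fits what is known about these is hard to picture, so this limb has almost no practical content here.
- A reader might infer that such an event would surface nowhere but the annual report. Under 10.4.3, SAEs outside the lists in 10.4.1 and 10.4.2 reach the Trial Office within 24 hours. The Chief Investigator reviews the event, and the DMC may do so. For the admissions listed in 10.4.2 the limit is four weeks, so the 24-hour point does not cover those.

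**Conclusion.** The inconsistency is real. For a related serious reaction that is listed in the RSI but has a discordant severity or outcome, Table 5 gives a SUSAR and Table 7, applied as written, does not. What could be lost is reporting to the MHRA and ethics committee on the regulatory timelines. Oversight inside the trial and inclusion in the DSUR are not lost.

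The size cannot be put as a number. The protocol gives no rate of serious reactions, and how many listed reactions could depart from their description depends on a product summary that is not part of the documents. The target of 705 children does not show how often the two tables would disagree. The affected group is narrow: related, serious, listed and discordant.

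The conclusion assumes that Table 7 is applied literally, as 10.5.2 instructs. It touches no estimand or analysis. It is a defect of wording in a safety rule, worth correcting because each affected event would be reported by a different route.

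**What to change.** Align Table 7 with the unexpected-reaction definition in Table 5. A related SAE would be expected only if its nature, severity and outcome are all consistent with the RSI; otherwise it is unexpected and a SUSAR. State in the same table that the wording on trial procedures does not apply to reactions attributed to cefalexin. Sections 10.1, 10.5.2 and 10.6 would then run on one rule. The pre-defined expectedness of the admissions in 10.4.2, which carries no severity or outcome qualifier, should be checked against that rule at the same time.

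The cost is a wording change to one table, with the amendment paperwork that goes with it, and possibly a few more events reported as SUSARs. No data collection changes, because severity is already assessed for SAEs and they are already followed to resolution or stabilisation.
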